	
 
• Unstable angina with need for outpatient treatment or hospitalization (change/addition of anti-anginal medication and/or coronary revascularization), within 3 calendar months prior to the consent date
 
• Angiographic evidence of coronary disease in a patient that is a candidate for coronary revascularization and is likely to undergo CABG or PCI in the next 3 calendar months
 
• High risk for arterial embolism (e.g. presence of mobile left ventricular thrombus)
 
• Hemodynamically significant congenital heart disease, aortic valvular heart disease, or amyloid heart disease
 
• Baseline body mass index <math>> 45 \text{ kg/m}^2</math>
 
• On a heart transplant list or likely to undergo heart transplant within one calendar year
 
• Presence of any other disease, other than the subject's cardiac disease, that in the opinion of the investigator is likely to significantly reduce the patient's likelihood of survival for the duration of the trial (e.g. cancer, liver failure).
 
• Unwillingness or inability to cooperate with the protocol
 
• Resides at such a distance from the enrolling site so travel to follow-up visits would be unusually difficult
 
• Reversible causes of heart disease (e.g. viral myocarditis or tachycardia induced cardiomyopathy)
 
• Participation in other clinical trials (observational registries are allowed with approval from the CDC)
 
• Does not anticipate residing in the vicinity of the enrolling site for the duration of the trial
 
• Unwillingness to sign the consent for participation
 

Statistical Methods	
Primary Statistical Hypothesis	Post-MI diabetes patients with a relatively preserved left ventricular ejection fraction will have reduced mortality from S-ICD as compared to CMT.
Statistical Test Method	Wang-Tsiatis group sequential design based on monitoring the log-rank statistic for time-to-death, with stochastic curtailment based on conditional power and sample size re-estimation based on overall recruitment, withdrawal, and event rates.
Sample Size Parameters	1800 patients are expected to yield a maximum of 454 deaths, which provides 80% power at a two-sided significance level of 5% to detect a HR of 0.75.

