#### 12.1.1.2. Sample Size

[figure not shown]
1800 men and women from the U.S., Europe, and Israel will be enrolled based on the following assumptions:

- **Wang-Tsiatis ( $\Delta=0.1$ ) Design with K=18 Possible Analyses**
- **2:1 randomization (S-ICD:CMT)**
- **$\alpha = 5\%$  (two-sided)**
- **Power = 80%**
- **Hazard ratio of 0.75**
- **Attrition rate of 10%**

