#### 12.1.1.3. Statistical Methods

A plot of the log-rank statistic versus its variance ('information') will be carried out periodically. At 18 pre-specified information times the log-rank statistic will be compared with pre-specified stopping boundaries, as indicated in Figure 12-1. If the boundary of A or B is reached prior to the final (18th) analysis, the trial will be terminated at that time. Otherwise, it will be continued until either (1) the maximum information level is reached, or (2) continuing the trial is determined to be futile based on current estimates of conditional power and projected trial termination (as discussed below).

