**Figure 12-1: Stopping and Decision Boundaries for the Design**

**AAA:** S-ICD more effective    **BBB:** Med Rx more effective    **CCC:** no difference

Reaching the upper boundary (A) leads to a decision in favor of the S-ICD, reaching the lower boundary (B) in favor of the medical treatment, and reaching the central part (C) of the vertical boundary results in a ‘no difference’ conclusion. Hence, a no-difference conclusion is only possible at the final analysis.

Numerical values of the boundaries, derived using SAS version 9.4, are in **Table 12.1-1**, along with the schedule of cumulative  $\alpha$ -spending and cumulative power for hazard ratios (HR’s) of 0.70 and 0.75. The cumulative power reaches 80% at analysis 18 for a HR of 0.75. For a HR of 0.70, the cumulative power exceeds 80% by analysis 14 and reaches 94% at the final analysis. Although this design could require as many as 454 events to

get to the final (18th) analysis, the trial would be expected to terminate at the 13th analysis if the HR is 0.75 and at the 10th analysis if the HR is 0.70.

**Table 12.1-1: Coordinates of the Upper and Lower Stopping Boundaries and the Associated  $\alpha$ -Spending and Cumulative Power**

Analysis (Info %)	Variance	Events	Standardized Boundaries ( $\pm$ )	Nominal $\alpha$	$\alpha$ -Spending	Cumulative Power HR=0.75 HR=0.70	
1 (15)	15.1	68.0	4.62	0.00000	0.00000	0.0002	0.0006
2 (20)	20.1	90.6	4.12	0.00004	0.00004	0.0024	0.0060
3 (25)	25.2	113.3	3.77	0.00017	0.00018	0.0106	0.0250
4 (30)	30.2	136.0	3.50	0.00046	0.00054	0.0292	0.0649
5 (35)	35.3	158.6	3.29	0.00100	0.00122	0.0611	0.1273
6 (40)	40.3	181.3	3.12	0.00181	0.00230	0.1062	0.2081
7 (45)	45.3	204.0	2.98	0.00292	0.00386	0.1626	0.3001
8 (50)	50.4	226.6	2.85	0.00433	0.00590	0.2272	0.3960
9 (55)	55.4	249.3	2.75	0.00602	0.00846	0.2966	0.4893
10 (60)	60.4	271.9	2.65	0.00799	0.01150	0.3677	0.5759
11 (65)	65.5	294.6	2.57	0.01020	0.01502	0.4377	0.6532
12 (70)	70.5	317.3	2.49	0.01263	0.01898	0.5047	0.7201
13 (75)	75.5	339.9	2.43	0.01526	0.02334	0.5675	0.7766
14 (80)	80.6	362.6	2.36	0.01806	0.02806	0.6250	0.8235
15 (85)	85.6	385.3	2.31	0.02102	0.03314	0.6770	0.8617
16 (90)	90.6	407.9	2.26	0.02410	0.03850	0.7234	0.8924
17 (95)	95.7	430.6	2.21	0.02729	0.04414	0.7643	0.9169
18 (100)	100.7	453.2	2.16	0.03058	0.05000	0.8000	0.9361

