### 12.1.1.3.2 Computations for Sample Size Expected to Generate 454 Events

Computation of a sample size that would be expected to generate 454 events depends on:

- (1) The number of patients recruited each month:  $P_1$  in month 1,  $P_2$  in month 2, ...
- (2) The overall event rate. If the 3-year cumulative event rate is 25% in CMT-only patients, and the HR is 0.75, then the overall rate is a weighted average (due to 2:1 randomization) of 0.25 (weight = 1) and  $1 - (1 - 0.25)^{0.75} = 0.194$  (weight=2). That works out to 21.3% over 3 years, or a monthly event rate (MER) of 0.59%.
- (3) The 5-year cumulative drop-out rate of 10% in each arm. That is a monthly drop-out rate (MER) of 0.17%.

In the first month,  $P_1$  patients are enrolled, and assuming uniformly distributed enrollment times, they are expected to contribute  $P_1/2$  months of follow-up. The expected numbers of events and withdrawals at the end of the first month are then  $(P_1/2)*MER$  and  $(P_1/2)*MDR$ , respectively. The expected number of patients remaining at risk entering month 2 is then  $P_1*(1 - MER/2 - MDR/2)$ . These monthly computations can be done sequentially, where at month  $j$ :

- $R_{j-1}$  patients are still at-risk from month  $j-1$
- $P_j$  patients are enrolled uniformly in month  $j$
- Expected follow-up time in month  $j$ :  $R_{j-1} + P_j/2$
- Expected numbers of events in month  $j$ :  $(R_{j-1} + P_j/2)*MER$
- Expected withdrawals in month  $j$ :  $(R_{j-1} + P_j/2)*MDR$
- Expected number of patients remaining at risk entering month  $j+1$ :  $R_{j-1}*(1 - MER - MDR) + P_j*(1 - MER/2 - MDR/2)$ .

Setting  $P_j = 25$  for  $j = 1, \dots, 12$ ,  $P_j = 35$  for  $j = 13, \dots, 24$ ,  $P_j = 45$  for  $j = 25, \dots, 48$ , and  $P_j = 0$  for  $j > 48$ , the expected counts that appear in Table 27.3-1 are obtained.

Table 27.3-1 in the Appendix provides a monthly accounting of patients with projections of events (assuming a HR of 0.75 and a 25% rate in (2)), withdrawals, and timing of analyses for this design. The 1st analysis should be performed at 15% information (69 events) and is projected to occur at month 30 with 990 patients enrolled. Further analyses would be performed at 5% increments of information (every 23 events), and these are expected to occur approximately every 3-4 months.

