### **12.3. Data Analyses**

Statistical tests of the difference in the primary endpoint (rate of all-cause mortality) between the randomized S-ICD and CMT groups will be computed by the unblinded statistician at periodic intervals during the trial and submitted to the Data Safety Monitoring Board (DSMB) as part of the group sequential design, and at the conclusion of the study (see section 12.1.1.3). The primary analysis will be based on statistical evaluation comparing the life-table time-to-event curves for S-ICD and CMT arms of the trial, the graphs being constructed by the method of Kaplan and Meier. The stratified log-rank test (stratified by enrolling site) will be used to evaluate statistical significance, adjusted for the group-sequential stopping rule of the trial with maximum-likelihood ordering; late-reported data will be appropriately incorporated. The hazard ratio for S-ICD relative to CMT, based on Cox proportional hazards modeling, will likewise be estimated. Also, 95% confidence limits for this hazard ratio will be determined, likewise adjusted for the sequential design.  
30

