#### **12.3.1. Other Objectives/Measurements**

The secondary objective of the study will evaluate the effects of the S-ICD on all-cause mortality in various subgroups and on sudden cardiac death. Sudden cardiac death will be analyzed using methods similar to those for all-cause mortality, except that they will be performed without adjustment for the sequential design. Sudden cardiac death events in the study will be independently adjudicated by the Mortality Events Committee using the Hinkle-Thaler criteria (see Appendix 28.4).

The pre-specified subgroups include but are not limited to: gender, race, age continuous and dichotomized at 75 years, duration of diabetes, presence versus absence of insulin therapy, HbA1c < 8% or ≥ 8%, LVEF continuous and dichotomized at 40%, MADIT II risk score subgroups. For each subgroup analysis, the Cox proportional-hazards regression analysis will be used to evaluate differences between subgroups in the hazard ratios (S-ICD vs. CMT). The baseline covariate or stratum and its interaction with treatment group will be added to the regression model and a test for significant interaction carried out. Each analysis will be stratified by enrolling site, where appropriate. These analyses will be done without

adjustment for the sequential design. Subgroup analyses are further described in section 12.3.3.

Pre-specified tertiary analyses include the following:

1. Frequency and outcomes of S-ICD treated episodes of ventricular tachycardia (VT) and ventricular fibrillation (VF).
2. Frequency and outcomes of S-ICD inappropriate shocks.
3. Frequency of S-ICD device complications, including but not limited to: infection, device malfunction and electrode movement.
4. Healthcare utilization assessed through adverse event reporting.

Tertiary analyses will be descriptive and exploratory. Detailed statistical methods for these outcomes will be presented in a Statistical Analysis Plan (SAP) prior to study termination.

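### Leaving sudden cardiac death unadjusted for the sequential design biases its hazard ratio, because the all-cause statistic that stops the trial contains those deaths

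*Combined protocol and SAP*

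**What the plan says.** The primary endpoint is death from any cause (section 7.1). Section 12.1.1.3 sets the monitoring rule: "At 18 pre-specified information times the log-rank statistic will be compared with pre-specified stopping boundaries". Reaching boundary A or B ends the trial. Section 12.1.1.2 specifies a Wang-Tsiatis (Δ = 0.1) "Design with K=18 Possible Analyses".

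For the primary analysis, section 12.3 says the site-stratified log-rank test "will be used to evaluate statistical significance, adjusted for the group-sequential stopping rule of the trial", and it adjusts the 95% confidence limits in the same way. Whether the Cox point estimate is also adjusted is not explicit.

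SCD is part of the secondary objective (section 6.2). Section 12.3.1 gives it similar methods, "except that they will be performed without adjustment for the sequential design". The subgroup analyses, described there as Cox models with a treatment-by-covariate interaction test, are also unadjusted. No reason, significance level or testing order is given for SCD. Only the tertiary analyses are called descriptive and exploratory.

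**The concern.** SCDs are a subset of the deaths that drive stopping. When the all-cause score crosses boundary A, its SCD component tends to be high too, partly by chance. The plan corrects the all-cause test and limits for this but leaves the SCD result as it stands.

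This matters because SCD prevention is the route by which the device is expected to lengthen life (sections 4, 19.5 and 19.6), and because early stopping is the expected course: section 12.1.1.3 projects termination at the 13th analysis if the HR is 0.75 and the 10th if it is 0.70. An unadjusted SCD hazard ratio would then stand beside adjusted all-cause limits, and a reader could take part of the stopping artefact for a larger effect on SCD.

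**Working it through.** **Inputs from the plan.** The design "this design could require as many as 454 events" (453.2 in Table 12.1-1), "which provides 80% power at a two-sided significance level of 5% to detect a HR of 0.75". Randomisation is 2:1. The looks are at 15%, 20%, …, 100% information.

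**Assumption.** SCD contributes a share f of the all-cause information, with f = 30% to 70%. Site stratification and the futility rule are ignored; Table 12.1-3 gives only a 2.1% chance of declaring futility at HR 0.75.

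**Step 1: reproduce the design.** Variance = (1/3)(2/3) × events = (2/9) × 453.2 = 100.7, as tabled. Boundary at information fraction t: 2.1627 × t^(0.1 − 0.5). This gives 4.62 at t = 0.15, 2.85 at t = 0.50 and 2.16 at t = 1, and it matches all 18 tabled values to two decimals. Simulating the 18-look score process gives:

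| | Table 12.1-1 | Simulated |
|---|---|---|
| Two-sided alpha | 0.0500 | 0.050 |
| Power, HR 0.75 | 0.8000 | 0.800 |
| Stopped before look 18, HR 0.75 | 0.7643 | 0.764 |
| Stopped by look 8, HR 0.75 | 0.2272 | 0.227 |

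**Step 2: the mechanism.** Write the all-cause score as S = S_scd + S_other, with independent parts, information V_scd = fV and V_other = (1 − f)V, and θ = fθ_scd + (1 − f)θ_other, where θ is minus the log HR. Given the path of S,

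E[S_scd − θ_scd·V_scd | S] = (V_scd/V)(S − θV).

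Dividing by V_scd shows that the mean error in the SCD log HR equals the error in the all-cause log HR at the stopping look. It does not depend on f.

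**Step 3: size at all-cause HR 0.75.** The SCD log HR and its nominal 95% interval were read at the all-cause stopping time. Positive bias means towards benefit. The third column shows a true SCD HR of 0.75 as 0.75 × exp(−bias).

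| Trials | Mean log-HR bias | 0.75 reported as | Coverage |
|---|---|---|---|
| All | 0.041 | 0.72 | 94.1–94.6% |
| Stopped by look 8 (23%) | 0.24 | 0.59 | 85–90% |
| All stopped before look 18 (76%) | 0.092 | 0.68 | 95.3–95.5% |
| Reached look 18 (24%) | −0.125 | 0.85 | 90–92% |

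**Step 4: type I error.** With no effect on any death, the nominal 5% SCD test rejects in 5.3% (f = 30%) to 6.0% (f = 70%) of trials, and the mean SCD HR is 1.00. With no effect on SCD but an effect on other deaths, the worst case tried (all-cause HR about 0.85) gives 5.5% to 6.0% for f = 30% to 60%. A critical value of 1.99 to 2.02 instead of 1.96 would hold 5% when there is no effect on any death (f = 30% to 60%).

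**Step 5: does a simple correction work?** Subtract the estimated stopping bias of the all-cause log HR from the SCD log HR (f = 40%). The mean SCD HR moves from 0.720 to 0.746 when the truth is 0.75. It moves from 0.468 to 0.485 when SCD carries the whole effect and the truth is 0.487. Among stops by look 8 it moves only from 0.591 to 0.620 against 0.75, so it removes the average bias but little of the bias conditional on a very early stop.

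**The case against.** The best defence is that the inferential damage is slight and the choice is disclosed. Type I error rises by at most about one percentage point and overall coverage falls by less than one. SCD has no stated significance level, power or place in a hierarchy, so readers may treat its result as nominal. The SCD share is unknown. All of this stands, and it limits the point to a minor-to-moderate one.

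A reader might infer more: that the SCD p-value and interval are simply invalid, and most so whenever the trial stops early. The plan's own boundaries do not support that. Over all early stops at HR 0.75, coverage is about 95%; it falls short only for stops by about half information and, in the opposite direction, at look 18. Under the null, early-stopped trials do reject SCD in roughly a quarter to two-thirds of cases, but that conditions on the 4.4% of trials that already hold a false-positive primary result.

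A reader might also extend the point to the subgroup analyses. Sections 12.3.1 and 12.3.3 describe interaction tests, where the common stopping bias cancels. Only subgroup-specific hazard ratios, if reported, would carry it.

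What the defence does not answer is the estimate. A nominal label warns about the p-value; it does not tell a reader that the hazard ratio is shifted, or by how much.

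**Conclusion.** The point holds for the SCD hazard ratio. A stated rule leaves in it a bias that the plan's own sequential method could address: about 0.04 on the log scale on average at HR 0.75, about 0.24 for stops by Analysis 8, and about −0.125 at look 18. The log-HR bias does not depend on the assumed SCD share; the coverage and type I figures do, and are given for 30% to 70%. All figures assume the Table 12.1-1 boundaries and a constant SCD share of information. The effect on overall type I error and coverage is small. The primary analysis is untouched. This is a cheap improvement of minor-to-moderate weight.

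**What to change.** In section 12.3.1, add for SCD a stopping-adjusted hazard ratio, 95% interval and p-value, derived from the joint normal distribution of the SCD and all-cause log-rank statistics under the stopping rule. For the point estimate, a simple version shifts the SCD log HR by the all-cause stopping-bias correction; section 12.3 should then state how that correction is computed. Report these beside the unadjusted results and label the unadjusted ones nominal.

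Do not use the boundary at the stopping look as the SCD critical value. It cuts type I error to about 2.9%, widens intervals by about 30% on average at HR 0.75 and, with a 50% SCD share and an SCD HR of 0.75, lowers power from 44% to 17%.

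Interaction tests can stay unadjusted. If subgroup-specific hazard ratios are reported, note that they carry the same bias.

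The cost is some wording, a little programming and a slightly less favourable SCD estimate. Conduct, event count and primary alpha do not change.

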### 6.2. *Secondary Study Objective*

The secondary objective of the study is to evaluate the effects of the S-ICD on all-cause mortality in various subgroups and on sudden cardiac death.

The pre-specified subgroups include but are not limited to: gender, race, age continuous and dichotomized at 75 years, duration of diabetes, presence versus absence of insulin therapy, HbA1c dichotomized at 8%, LVEF continuous and dichotomized at 40% and MADIT II risk score sub-groups (MADIT II risk score: New York Heart Association functional class > II, age > 70 years, BUN > 26 mg/dl, QRS duration > 120 ms, and atrial fibrillation).

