## 8. Design

MADIT S-ICD is a prospective, multicenter, international, randomized (2:1), controlled clinical trial. Subjects (n=1800) will be enrolled at approximately 100 study sites and randomized to receive conventional medical therapy plus an S-ICD or conventional medical therapy alone in a 2:1 ratio, respectively. The trial uses a group sequential design with 18 pre-specified interim analyses. The sample size was chosen to detect a hazard ratio of 0.75 with 80% power (1- $\beta$ ), two-sided 5% significance level ( $\alpha$ ) and accounts for an estimated dropout rate of 10%. This trial will be conducted under an investigational device exemption (IDE) in the United States and as a post-market study in Europe and Israel.

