### **12.3.3. *Subgroup Analyses***

Interactions between treatment and important baseline variables will be investigated by including the appropriate interaction term in the statistical model and testing for its significance. The list of potential baseline variables to evaluate is listed below. Also included are dichotomous cut points if applicable (based on clinically meaningful cut point, historical use, or median value):

- Duration of diabetes > 2 years,
- Presence or absence on insulin therapy,
- Age  $\geq$  75 years,
- LVEF  $\leq$  45%,
- QRS  $\geq$  120 msec,
- Males vs. females,
- Caucasian (Non-Hispanic) vs other racial and ethnic categories,

- Small centers (<10 patients enrolled) vs. large centers ( $\geq 10$  patients enrolled)

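### HbA1c is named as an effect modifier only through a cut at 8%, although age and LVEF are also listed as continuous; if the modification is graded, the cut gives the weaker interaction test

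*Combined protocol and SAP*

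**What the plan says.** The secondary objective covers the S-ICD effect on all-cause mortality in pre-specified subgroups. Section 12.3.1 tests each one by adding the baseline covariate or stratum and its interaction with treatment to a Cox model, without adjustment for the sequential design.

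- **Section 12.3.1:** "HbA1c < 8% or ≥ 8%, LVEF continuous and dichotomized at 40%, MADIT II risk score subgroups". Age, earlier in the same sentence, is continuous and also cut at 75 years.
- **Section 6.2:** "HbA1c dichotomized at 8%, LVEF continuous and dichotomized at 40" (per cent). The synopsis repeats this form.
- **Section 12.3.3:** a list of potential variables that says dichotomous cut points are included where applicable. HbA1c is not in it. It shows "Duration of diabetes > 2 years", QRS at 120 msec or more, age at 75 years or more and LVEF at 45% or less.

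The subgroup lists in 6.2 and 12.3.1 are expressly open-ended. The documents give no interaction effect size, no power for any interaction test, no HbA1c distribution and no expected share of patients at or above 8%.

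**The concern.** Everyone in this trial has diabetes, so whether S-ICD benefit varies with glycaemic control is a natural secondary question. HbA1c is a continuous laboratory value. Cutting it at 8% treats 8.0 and 12.0 as the same and 7.9 and 8.0 as different, and it discards information if the effect changes gradually. The plan names a continuous form for age and LVEF in the same sentence but not for HbA1c, and it gives no reason for the difference. The general rationale for cut points in 12.3.3 does not reach HbA1c, which is absent from that list.

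Interaction information is limited by the number of deaths, and the trial may stop before the maximum. What is at stake is that a real gradient across HbA1c is more likely to be reported as no significant interaction.

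**Working it through.** **Inputs from the documents.** Section 8: "The sample size was chosen to detect a hazard ratio of 0.75 with 80% power". Synopsis: "1800 patients are expected to yield a maximum of 454 deaths". Allocation is 2:1 (12.1.1.2). Table 12.1-1 gives 453.2 events and variance 100.7 at analysis 18.

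**Assumptions not in the documents.** Interaction tests at two-sided 5%; log hazard ratio linear in HbA1c; HbA1c about normal; hazard-ratio ratio per SD between 0.75 and 0.90; 30% to 50% of patients on the smaller side of the cut; no stratification by site.

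**Step 1: the plan's own figure.** Fixed-design events are (1.960 + 0.842)² / [(ln 0.75)² × 2/9] = 7.849 / 0.01839 = 427. Recursive integration over the 18-look Wang-Tsiatis boundary (Δ = 0.1) gives a first bound of 4.62, a final bound of 2.16 and 453.3 events for 80% power. The plan's statement that "The cumulative power reaches 80% at analysis 18 for a HR of 0.75" is reproduced. The variance also agrees: 453.2 × 2/9 = 100.7.

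**Step 2: continuous interaction test.** For a covariate in SD units, the expected z is √(454 × 2/9) × |ln r| = 10.04 × |ln r|, where r is the hazard-ratio ratio per SD.

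**Step 3: effect of the cut.** With a share p on one side, the cut keeps φ(z_p)² / [p(1−p)] of the information: 0.637 at 50/50, 0.576 at 30/70, 0.490 at 20/80 and 0.342 at 10/90. The expected z shrinks by the square root of this.

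**Step 4: power at 454 deaths.**

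| r per SD | z, continuous | Power, continuous | Power, cut 50/50 (loss) | Power, cut 30/70 (loss) |
|---|---|---|---|---|
| 0.75 | 2.89 | 82.4% | 63.5% (18.9) | 59.2% (23.2) |
| 0.80 | 2.24 | 61.1% | 43.2% (17.9) | 39.8% (21.3) |
| 0.85 | 1.63 | 37.2% | 25.6% (11.6) | 23.6% (13.6) |
| 0.90 | 1.06 | 18.5% | 13.5% (5.0) | 12.6% (5.8) |

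A 20/80 split at r = 0.75 gives 52.5%, a loss of 29.9 points. At 340 deaths (Analysis 13, where the plan expects to stop if the HR is 0.75), r = 0.85 gives 29.2% against 20.3% and 18.8%, a loss of 9 to 10 points.

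**Step 5: simulation check.** Cox models were fitted to 1,800 simulated patients, 2:1, at 454 deaths, 1,500 replicates per setting. With a linear effect of 0.28 on the log scale per SD (ratio 0.76), the loss was 18.1 points (50/50) and 20.1 points (30/70) for a normal covariate, and 23.9 and 22.2 points for a log-normal one. With 0.15 per SD (normal, 50/50) it was 10.8 points.

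**Step 6: the opposite case.** With a true step at the cut of 0.56 (50/50) or 0.61 (30/70) on the log scale, simulated power was 63% continuous against 83% cut, and 68% against 85%. The cut therefore gains about 17 to 20 points. For a smaller step, a ratio of 0.75 between the two subgroup hazard ratios, the formula gives 21% against 30% (50/50) and 17% against 26% (30/70), a gain of about 9 points.

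**The case against.** **The plan leaves room already.** The subgroup list is open, the model accepts a covariate or a stratum, and 12.3.7 allows an amended SAP before study completion. So continuous HbA1c is not excluded. That stands, but a test added later is not a named, pre-specified one, and where the plan intends a continuous form it says so.

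**The size of the loss is not a property of this plan.** That also stands. A reader might infer a fixed loss of about 18 to 24 points. That range needs a continuous test with roughly 60-85% power, a linear effect and a split between 30/70 and 50/50. At 454 deaths, 80% power requires a ratio near 0.75 per SD, an interaction as large as the main effect assumed for the trial. With weaker modification both tests are weak and the loss is small. The 64% figure also depends on normality: for a uniform covariate a median cut keeps 75% (0.5² × 0.25 ÷ 1/12).

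**A step at 8% would reverse the result.** True, as step 6 shows. No section posits such a step, but it is a good reason to keep the cut test.

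**QRS and diabetes duration.** A reader might infer from 12.3.3 that these too will be tested only as cuts. The text does not support that. The same list shows age and LVEF only as cuts, although 12.3.1 lists both as continuous. Duration of diabetes carries no cut in the synopsis, 6.2 or 12.3.1. In 6.2, QRS appears only inside the MADIT II risk score.

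**Conclusion.** The concern holds for HbA1c. All three places that name it as a subgroup variable give only the 8% cut, beside age and LVEF in both forms. Under a roughly linear effect and a near-normal HbA1c, the cut keeps 58-64% of the interaction information for splits of 30/70 to 50/50. It then costs about 5 to 23 points of power at 454 deaths for ratios of 0.90 to 0.75 per SD. More uneven splits cost more. A true threshold at 8% turns the loss into a gain for the cut. Since the documents give neither an interaction size nor an HbA1c distribution, no single figure should be quoted without these conditions.

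This is a minor point about the sensitivity of one secondary analysis. It does not touch the primary analysis, the alpha spending, the sample size or the stopping rules, and in simulation each interaction test had type I error of about 5%.

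**What to change.** - In the synopsis, 6.2 and 12.3.1, list *HbA1c continuous and dichotomized at 8%*.
- In 12.3.1, name treatment × continuous HbA1c in the Cox model as the main HbA1c interaction test. Fix any transform in advance and do not choose it after seeing the data.
- Keep the 8% cut test and the subgroup hazard ratios beside it, so that HbA1c has both forms as age and LVEF do.
- Optionally, for consistency, state in 12.3.3 that QRS and duration of diabetes are also tested as continuous terms. The present text does not rule this out.

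The cost is wording only: the continuous test uses the value already needed for the cut, with no extra patients or visits. The downsides are one more secondary interaction test, and less power from the linear term if the modification is a threshold at 8%, a case the retained cut test addresses.
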